8.4.8 PHQ-4

The PHQ-4 is a simple 4 item measure of anxiety (2 items) and depression (2 items) (24). Each item is scored on a 4-point (0-3) NRS and the items are summed to give a total score ranging from 0-12. The total score provides an assessment of psychological distress. The 2-item anxiety and depression scales can also be scored and scores of 3 or greater are considered positive for screening purposes. The PHQ-4 will be measured at baseline in the Phase 1 pre-treatment run-in period, week 16 (Phase 3), week 38, and at week 64 in the LTE.

8.4.9 Adequate Relief Question

The following question will be asked during week 16, 38, and 64 via the Curebase data collection (ePRO) system:

- On average, over the past 2 weeks have you had adequate relief of your IBS symptoms? (Y/N)

8.4.10 Satisfaction Questions

The following questions will be asked during the last week of Phase 3 (week 16) via the Curebase data collection (ePRO) system:

- Overall, how satisfied were you with the therapy you received? (1-5 scale)
- Would you recommend the therapy you received to someone with IBS? (Y/N)
- Would you recommend using the therapy you received before trying a prescription drug? (Y/N)

8.5 Safety and Other Assessments

Safety will be assessed using AE reporting (see [Section 9.3](#)).

8.5.1 Concomitant Medication/Therapy

Concomitant medications and treatment will be collected at the baseline screening visit, week 8 and week 16. Concomitant medications and treatment use will also be collected at week at 38 and 64 in the LTE. The following information will be collected:

1. Concomitant Medications
 - a. Medication name
 - b. Indication
 - c. Medication form (e.g., tablet, capsule, etc.)
 - d. Medication dose units (e.g., gram, IU, etc.)
 - e. Medication schedule (e.g., QD, BID, etc.)
 - f. Start date
 - g. End date
2. Non-medication Therapy

- a. Indication
- b. Schedule/Frequency (daily, weekly, monthly, other)
- c. Type of therapy
 - i. Physical therapy
 - ii. Occupational therapy
 - iii. Psychotherapy (talk therapy)
 - iv. Cognitive Behavioral therapy (CBT)
 - v. Counselling
 - vi. Guided self-help
 - vii. Behavioral activation
 - viii. Mindfulness therapy
 - ix. Other
- d. Start date
- e. End date

8.5.2 Blinding Assessment

Subject blinding will be assessed in the last week of Phase 3 using the following question:

Even if you do not feel you received benefit from your treatment program, do you believe the program you received could be beneficial to others with IBS?

Answers will be on a 7-point NRS, with the following guidelines:

- 1 – Definitely could not help others with IBS
- 4 – May or may not help others with IBS
- 7 – Definitely could help others with IBS

Given that this study is hypothesis blinded, the blinding assessment is designed to assess the credibility of the treatment and the credibility of the comparator as a treatment for IBS.

8.6 Adverse Events and Serious Adverse Events

8.6.1 Definition of Adverse Events

Adverse event¹ means any untoward medical occurrence, unintended disease or injury, or untoward clinical signs in subjects, whether or not related to the investigational medical device (21 CFR 312.32 (a)).

In the context of the investigational device, an AE constitutes:

- any unintentional, unfavorable clinical sign or symptom, including complications of IBS (but not IBS itself).
- any new illness or disease or the deterioration of existing IBS

¹ ISO14155 and 21 CFR 812

- any clinically significant deterioration in any clinical assessment or outcome measure
- Any adverse event resulting from insufficiencies or inadequacies in the instructions for use, the deployment, the installation, the operation or any malfunction of the investigational medical device. This includes any event that is a result of a use error or intentional abnormal use of the investigational medical device

Pre-existing conditions (unless worsened significantly during treatment) or routine diagnostic and therapeutic procedures normally administered in the treatment of IBS do not constitute AEs. AEs will be collected from the time a subject signs the informed consent until study withdrawal, screen failure, or study completion.

If the subject experiences a worsening or complication of an AE after ongoing treatment, the worsening or complication should be recorded as a new AE. Investigators should ensure that the AE term recorded captures the change in the condition (e.g., “worsening of...”).

In this study, it is possible that some subjects may experience a worsening of IBS symptoms. As the primary endpoint of this study, worsening of IBS symptoms is captured as part of the efficacy parameter. Worsening of IBS symptoms should not be considered an AE unless the worsening of the symptoms is associated with a cause other than the subject’s IBS.

All AEs that occur in study subjects during the AE reporting period specified in the protocol must be reported, WHETHER OR NOT THE EVENT IS CONSIDERED RELATED TO THE STUDY TREATMENT.

NONSERIOUS AEs are to be documented on the AE CRFs.

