	
Secondary Objectives
 
• To demonstrate that Regulora has a positive impact on relief of IBS symptoms, quality of life, workplace performance (presenteeism and absenteeism), and psychological distress relative to MR therapy.• To determine the durability of Regulora in relief of IBS symptoms, quality of life, workplace performance (presenteeism and absenteeism), and psychological distress relative to MR therapy. 
Exploratory Objective
 
The exploratory objective of this study is to investigate predictors of treatment success using the PHQ-4 and Thought Impact Scale (TIS).

Endpoints:	
Primary Endpoint: The primary endpoint of this study is abdominal pain intensity. The Instrument is a 0-10 numeric rating scale (NRS, 0= no pain, 10= worst pain). The subject is asked to record their “worst abdominal pain over the past 24-hours”. An Abdominal Pain Intensity Responder is defined as a subject whose daily abdominal pain intensity averaged over the 4 weeks of Phase 3 (weeks 13 through 16) is 30% reduced compared to the daily abdominal pain intensity averaged over the 4 weeks of Phase 1 (weeks -4 through -1).
 
Secondary Efficacy Endpoints: The secondary efficacy endpoints of this study include:
 
• Overall mean change from Phase 1 to Phase 3 and Phase 1 to Phase 4 (LTE) in:
○ Abdominal pain intensity○ Abdominal pain frequency○ Irritable Bowel Syndrome-Quality of Life questionnaire (IBS-QOL)○ Daily stool consistency (IBS-D and IBS-M)○ Daily stool frequency (IBS-C)○ Workplace Productivity and Activity Impairment questionnaire (WPAI)• 12-week trends during Phase 2 in:
○ Abdominal pain intensity○ Abdominal pain frequency○ Daily stool consistency

	
○ Daily stool frequency 
Secondary Safety Endpoints: Safety and tolerability will be evaluated by comparing adverse events in the treatment arm versus comparator arm.
 
Exploratory Endpoints:
 
● Prediction of treatment success using the North Carolina Thought Impact Scale (TIS)● Prediction of treatment success using the PHQ-4● Treatment adherence (number of sessions completed)● Concomitant IBS Medication● Blinding Assessment● Satisfaction questions● IBS-Adequate relief (IBS-AR)

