2.3 Schedule of Activities

The complete schedule of study activities, often referred to as a “Time and Events” (T+E) table, is presented in [Table 1](#). Please observe the following when interpreting it:

- The **Phase 1 run-in period** will start the day after the **Baseline Visit**.
- The **Onboarding Call** will occur as soon as possible (at least 1 day but not more than 14 days) after the Phase 1 run-in period. The call will take place on the next mutually agreeable non-holiday weekday.
- Randomization occurs on the day of the Onboarding call, which we define as “Day 0” in our framework.
- **Phase 2 (treatment)** will begin no more than 7 days after the Onboarding call.
- As part of ensuring the above schedule of activities are completed in a timely manner and in accordance with the protocol, the study team shall utilize phone call, email, and text-based reminders sent to the study subjects.

Please refer to [Section 8](#) for a detailed description of assessments described in [Table 1](#).

	Online Screening	Baseline Visit	Run-In Period (weeks -4 to -1)	Onboarding Call day 0	Treatment Period (weeks 1-12)	Run-Out Period (weeks 13-16)	LTE 1: (weeks 35-38)	LTE 2: (weeks 61-64)
Informed Consent	X							
Diagnosis (Rome IV)		X						
Inclusion Exclusion Criteria		X						
Abdominal Pain Severity			Daily		Daily	Daily	Daily	Daily
Randomization				X				
Screening & Onboarding				X				
Treatment Adherence Data (Wistia)					Continuous import			
Stool Consistency			Daily		Daily	Daily	Daily	Daily
Stool Frequency			Daily		Daily	Daily	Daily	Daily
Adverse Event Reports			X	X	X	X	X	X
IBS QOL		X				Once at week 16	Once at week 38	Once at week 64
TIS		X						
WPAI		X			Once at week 8	Once at week 16	Once at week 38	Once at week 64
Concomitant medication assessment		X (checked)			Once at week 8	Once at week 16	Once at week 38	Once at week 64

		by physician)					
PHQ-4			X			Once at week 16	Once at week 38
Satisfaction Survey						Once at week 16	
Blinding assessment						Once at week 16	

Table 1 Schedule of Activities

Abbreviations: IBS QOL=Irritable Bowel Syndrome Quality of Life Questionnaire; LTE=long-term extension; PHQ-4=Patient Health Questionnaire-4; TIS=North Carolina Thought Impact Scale; WPAI =Workplace Productivity and Activity Impairment Questionnaire.

Participants are asked to complete their Baseline Surveys within 7 days of enrollment, which include IBS QOL, PHQ4, TIS, and WPAI.

TABLE OF CONTENTS

1	ADMINISTRATIVE INFORMATION												

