8.6.4 Time Period and Frequency for Event Assessment and Follow-Up

The occurrence of an AE or SAE may come to the attention of study personnel during study visits and interviews of a study subject presenting for medical care, or upon review by a study monitor.

All AEs including not meeting the criteria for SAEs will be captured on the appropriate eCRF. Information to be collected includes event description, date of onset, clinician's assessment of severity, relationship to study product (assessed only by those with the training and authority to make a diagnosis), and date of resolution/stabilization of the event. All AEs occurring while on study must be documented appropriately regardless of relationship. All AEs will be followed to adequate resolution.

Any medical condition that is present at the time that the subject is screened will be considered as baseline and not reported as an AE. However, if the study subject's condition deteriorates at any time during the study, it will be recorded as an AE.

Changes in the severity of an AE will be documented to allow an assessment of the duration of the event at each level of severity to be performed. AEs characterized as intermittent require documentation of onset and duration of each episode.

The study team will record all events with start dates occurring any time after informed consent is obtained through the end of Phase 4 (LTE) or until the end of study participation.

Events will be followed for outcome information until resolution or stabilization.

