9.3 Populations for Analyses

Enrolled Population: The enrolled population will include all subjects who sign informed consent and meet the inclusion/exclusion criteria. This population will be used for evaluation of demographics and baseline characteristics.

Intent-to-Treat (ITT) Population: The ITT population will include all subjects who are randomized to treatment. Subjects that are replaced due to failed inclusion/exclusion criteria or technical issues in the Curebase software will be excluded. This population will be used for the evaluation of efficacy and all safety analyses.

Per Protocol (PP) Population: The PP population will consist of all subjects in the ITT population with no major protocol deviations that may affect efficacy. This population will be used as a supportive analysis of the primary endpoint.

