9.4.5 Safety Analyses

All AEs will be coded to System Organ Class (SOC) and Preferred Term using Medical Dictionary for Regulatory Activities (MedDRA). The number and percentage of subjects that experience at least one AE, grade 3-5 AEs, related AEs, SAEs, and related SAEs will be summarized by treatment group. Additionally, AEs will be summarized by severity and relatedness.

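### The by-arm adverse event summary has no onset window, so the all-cause any-AE percentages include events before the first session and up to 52 weeks after treatment

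*Combined protocol and SAP*

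**What the plan says.** - **Collection.** Section 8.6.1: "AEs will be collected from the time a subject signs the informed consent until study withdrawal, screen failure, or study completion". Section 8.6.4 is more explicit. The study team is to "record all events with start dates occurring any time after informed consent is obtained through the end of Phase 4 (LTE"), or until participation ends. Table 1 lists AE reports for the run-in, the onboarding call, treatment, run-out and both LTE assessment periods.
- **Analysis.** Section 9.4.5: "The number and percentage of subjects that experience at least one AE, grade 3-5 AEs, related AEs, SAEs, and related SAEs will be summarized". These counts are split by arm, and there are further summaries by severity and relatedness. The section defines no treatment-emergent event, risk window or split by phase.
- **Population.** Section 9.3 says of the ITT population: "This population will be used for the evaluation of efficacy and all safety analyses". Screen failures are therefore outside the tables, but run-in events of subjects who are later randomised are inside.
- **Role.** The Synopsis and Section 4.2.2 make this the safety endpoint: "Safety and tolerability will be evaluated by comparing adverse events in the treatment arm versus comparator arm". The Synopsis also says that safety is summarised descriptively.
- **Timing.** Section 2.3: "Randomization occurs on the day of the Onboarding call", which follows the 4-week run-in by 1 to 14 days. Treatment "will begin no more than 7 days after the Onboarding call".

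**The concern.** The headline safety measure is binary per subject: at least one AE, or none. A subject who catches a cold during the run-in is already counted, so a later event on treatment cannot change that subject's entry in the any-AE row. The same holds in reverse for a first event many months after the last session. Time in which neither arm is being treated raises both percentages and draws them together.

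Being safe is part of the hypothesis in Section 5.1, and the between-arm AE comparison is how the protocol says safety will be judged. A reader of the any-AE row would see a smaller relative contrast than arose on treatment. Several of the anticipated events in Section 8.6.3.5, such as headache, fatigue and gastrointestinal discomfort, also occur without treatment, so they are open to this dilution.

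**Working it through.** **1. The window.** The protocol states no AE rate, so there is no AE figure to reproduce. Its stated duration of 68 weeks does reproduce, as 4 (run-in) + 12 (treatment) + 52 (week 64 minus week 12).

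| Part of the window | Weeks | Share of 68 |
|---|---|---|
| Before treatment | 4 | 5.9% |
| Treatment | 12 | 17.6% |
| After treatment | 52 | 76.5% |

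The scheduling allowances in Section 2.3 lengthen the first row: 28 + 14 + 7 = 49 days, or 7 weeks. The window is then 7 + 12 + 52 = 71 weeks, of which 12/71 = 16.9% is treatment. The interval from consent to the baseline visit comes on top. Its length is not stated, and it can be zero because Section 10.1.1 lets a subject delay signing until the visit.

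Sections 2.1 and 5.1 give Phase 4 as 52 weeks, and the Synopsis also starts it after Phase 3. On that reading the total is 4 + 12 + 4 + 52 = 72 weeks and follow-up reaches 56 weeks after treatment. The conclusion is the same.

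**2. Dilution from pre-treatment events alone.** Let a be the probability of a pre-treatment AE, equal in the two arms, and t the on-treatment probability, independent of a. Then

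any-AE = 1 − (1 − a)(1 − t), and the tabulated difference = (1 − a)(t_GDH − t_MR).

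Assumed, not from the documents: t = 20% (GDH) and 10% (MR), so the true ratio is 2.0 and the true difference is 10 points.

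| a | GDH | MR | Ratio | Difference |
|---|---|---|---|---|
| 5% | 1 − 0.95 × 0.80 = 24.0% | 1 − 0.95 × 0.90 = 14.5% | 1.66 | 9.5 points |
| 10% | 1 − 0.90 × 0.80 = 28.0% | 1 − 0.90 × 0.90 = 19.0% | 1.47 | 9 points |
| 20% | 1 − 0.80 × 0.80 = 36.0% | 1 − 0.80 × 0.90 = 28.0% | 1.29 | 8 points |

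**3. Adding the post-treatment period.** This needs stronger assumptions: a constant background rate in both arms and a GDH excess of 10 points confined to the 12 treatment weeks. With b the 12-week MR risk, the probability of no event in the 4 + 52 = 56 untreated weeks is s = (1 − b)^(56/12). The tabulated risks are 1 − (1 − b)s for MR and 1 − (1 − b − 0.10)s for GDH.

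| b | On-treatment ratio | MR, whole window | GDH, whole window | Ratio | Difference |
|---|---|---|---|---|---|
| 5% | 3.0 | 25.2% | 33.1% | 1.31 | 7.9 points |
| 10% | 2.0 | 45.0% | 51.1% | 1.14 | 6.1 points |
| 20% | 1.5 | 71.8% | 75.3% | 1.05 | 3.5 points |

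These rows illustrate direction and rough order. They are not predictions.

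**4. Which rows are affected.** The calculation applies to the all-cause any-AE row. Section 8.6.3.4 grades relatedness on timing relative to study treatment, so a run-in event could not reasonably enter the related-AE or related-SAE rows. Nor does a run-in cold stop the same subject from being counted later for an SAE, a grade 3-5 event or a related event.

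**The case against.** **The window governs collection, and the SAP may define the analysis set.** Broad collection is sound practice and is not criticised here. The Synopsis and the opening of Section 9 defer analysis details to a SAP, which could hold a treatment-emergent definition, but the combined document contains no such text. Sections 9.4.4 and 9.4.8 refer to the SAP themselves, and 9.4.5 does not. What stands is that 9.4.5 states no window. It does not state a rule that events must be pooled regardless of onset.

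**Baseline conditions are already excluded.** Section 8.6.4 treats conditions present at screening as baseline. That does not remove new events between consent and the first session.

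**Related events are tabulated separately.** This is a real mitigation and confines the problem mainly to the all-cause any-AE row. It rests on a causality judgement, which Sections 8.6.3.4, 8.6.3.5 and 8.6.5 place variously with a clinician, the sponsor and the Curebase team. An onset date needs no such judgement.

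**Nothing inferential depends on it.** A reader might infer that the plan is set up to conclude that GDH is safe, or that a safety test loses power. The documents support neither. Safety is descriptive, with no AE test, margin or threshold. Pre-randomisation events should balance between arms in expectation, so they dilute the contrast without favouring an arm.

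**The illustrated excess is assumed and the absolute change is small.** Both are fair. Section 3.3.1 reports treatment-related non-serious AEs below 1% in earlier hypnotherapy trials. Those are not all-cause rates, but they give no support for a 10-point excess. In step 2 the difference moves by only 0.5 to 2 points.

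**Whole-follow-up reporting is legitimate in a trial with durability objectives.** It is, and any effect that lasts or appears late would be signal in the LTE. That argues for showing LTE events in their own table.

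**Conclusion.** The point holds as a limited one. As Section 9.4.5 is written, the all-cause any-AE percentages by arm include events before randomisation and first treatment and up to 52 weeks after treatment, and this dilutes the descriptive contrast. Rows for related events are much less affected.

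The size depends on AE rates that the documents do not give. With pre-treatment AEs in 5% to 20% of subjects and true on-treatment rates of 20% against 10%, the ratio falls from 2.0 to between 1.66 and 1.29, and the difference from 10 points to between 9.5 and 8. Post-treatment events would dilute it further if the background rate is constant and any excess is confined to treatment. No misleading safety decision follows from this, since the plan contains no decision rule on AEs. It is a cheap improvement to the analysis text.

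**What to change.** Keep collection as it is in Sections 8.6.1 and 8.6.4. In Section 9.4.5:

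1. Make the main by-arm table events that start or worsen at or after the first session, through a post-treatment window stated in advance. The end of Phase 3 (week 16) is one natural choice because it closes the primary assessment period, but the end point is partly a matter of preference. What matters is that it is fixed before unblinding.
2. Tabulate events before the first session separately by arm.
3. Tabulate LTE events separately by arm, so that late events stay visible.
4. Say how randomised subjects who never start a session enter the main table, since the safety population is ITT.

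The cost is a few sentences and two extra tables. No new data are needed: Section 8.6.4 already requires onset dates, Section 8.6.1 has a worsening recorded as a new event, and the treatment platform logs session start times (Section 7.1.1). If the SAP already defines such a window, one cross-reference in 9.4.5 closes the point.

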4.2.1 Primary Endpoint

The primary endpoint of this study is abdominal pain intensity. The Instrument is a 11-point numeric rating scale (0= no pain, 10= worst pain). The subject is asked to record their “*worst abdominal pain over the past 24-hours*”. An Abdominal Pain Intensity Responder is defined as a subject whose daily abdominal pain intensity averaged over the 4 weeks of Phase 3 (weeks 13 through 16) is 30% reduced compared to the daily abdominal pain intensity averaged over the 4 weeks of the Phase 1 (weeks -4 through -1).

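### The protocol both counts and does not count worsening IBS as an adverse event, and no stated analysis counts worsened subjects by arm

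*Combined protocol and SAP*

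**What the plan says.** Section 8.6.1 opens its AE list with unfavorable signs and symptoms, "including complications of IBS (but not IBS itself"). The next bullets add "any new illness or disease or the deterioration of existing IBS" and "any clinically significant deterioration in any clinical assessment or outcome measure". A following paragraph excludes pre-existing conditions, except those that worsen significantly during treatment.

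Later in the same section the rule is reversed for IBS: "Worsening of IBS symptoms should not be considered an AE unless the worsening of the symptoms is associated with a cause other than" IBS itself. The reason offered is this: "As the primary endpoint of this study, worsening of IBS symptoms is captured as part of the efficacy parameter".

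Section 8.6.4 treats any condition present at screening as baseline, but if the subject's "condition deteriorates at any time during the study, it will be recorded as an AE". It does not mention IBS.

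The primary responder (Sections 4.2.1, 9.1 and 9.4.2) is a subject whose average pain in weeks 13-16 "is 30% reduced compared to the daily abdominal pain intensity" in Phase 1. Section 4.2.2 evaluates safety by comparing AEs between the arms, and Section 9.4.5 tabulates AEs only. Section 3.3.3 includes worsening of symptoms among the primary risks.

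**The concern.** The safety comparison needs one definition of an AE. Here a subject whose IBS gets worse is an AE under some sentences and not under others. Section 3.3.3 invites subjects whose symptoms worsen to call the CRO or a study physician, so staff can expect such reports and will have to classify them. If the rule is applied differently between staff, over time or between arms, the by-arm AE percentages for a risk the protocol itself names have no fixed meaning.

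The exclusion would matter less if the efficacy analysis counted the excluded events. The protocol says that it does. The question is whether any stated analysis shows, by arm, how many subjects got worse.

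**Working it through.** **1. The rules side by side.** Take a subject whose IBS worsens during treatment with no other cause identified.

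| Text | Is it an AE? |
|---|---|
| 8.6.1, first bullet | Complications yes, IBS itself no |
| 8.6.1, second bullet | Yes |
| 8.6.1, third bullet | Yes, if clinically significant (no threshold given) |
| 8.6.1, pre-existing conditions | Yes, if significantly worse |
| 8.6.1, later paragraph on IBS | No |
| 8.6.4 | Yes; every subject has IBS at screening and no exception is made |

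Two further points are open. Section 8.6.1 does not say whether worsening provoked by a treatment session has a cause other than IBS, yet it requires reporting regardless of relatedness. Section 8.6.3.5 lists GI discomfort as an anticipated AE, which may be hard to separate from IBS symptoms.

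**2. What the responder can show.** Take a subject at the entry floor of Section 6.2, Phase 1 average pain 3.
- Responder: Phase 3 average at or below 0.70 × 3 = 2.1.
- Unchanged at 3.0: non-responder.
- Worsened by 30%, to 1.30 × 3 = 3.9: non-responder.

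The last two get the same score. The endpoint also covers pain only, and only weeks 13-16.

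**3. The plan's own figure.** Inputs from Section 9.2: 300 completers (150 per arm), 26% against 26% + 18 points = 44%, two-sided 5%.
- Pooled rate 0.35; SE under the null = √(2 × 0.35 × 0.65 / 150) = 0.0551.
- SE under the alternative = √((0.26 × 0.74 + 0.44 × 0.56) / 150) = 0.0541.
- Power = Φ((0.18 − 1.96 × 0.0551) / 0.0541) = 0.909.

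This agrees with the stated 90% or more. Nothing here disputes the sample size.

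**4. Can a mean hide a worsened subgroup?** This is an illustration; all of its pain inputs are assumptions. Mean change is −2.5 in responders, 0 if unchanged and +1.5 if worsened; within-group variance is 0.64; 10% of MR subjects worsen. Responders are held at 44% and 26%, with 150 per arm. For responder fraction r and worsened fraction w:
- mean m = −2.5r + 1.5w
- variance v = 6.25r + 2.25w − m² + 0.64

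MR: m = −0.65 + 0.15 = −0.50; v = 1.625 + 0.225 − 0.25 + 0.64 = 2.24.

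GDH with 30% worsened: m = −1.10 + 0.45 = −0.65; v = 2.75 + 0.675 − 0.4225 + 0.64 = 3.6425.

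Difference −0.15; SE = √((3.6425 + 2.24) / 150) = 0.198; z = −0.76.

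| GDH worsened | Responder power | Mean difference | Expected z | Power of comparing worsened proportions |
|---|---|---|---|---|
| 10% | 0.909 | −0.45 | −2.48 | not applicable |
| 15% | 0.909 | −0.375 | −2.01 | 0.26 |
| 20% | 0.909 | −0.30 | −1.58 | 0.68 |
| 30% | 0.909 | −0.15 | −0.76 | 0.99 |

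Responder power is constant by construction: moving subjects from unchanged to worsened leaves the responder rate alone. The mean difference shrinks but still favours GDH when three times as many GDH subjects worsen.

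**5. Reach of a 30%-rise threshold.** On a 0-10 scale a 30% rise needs a Phase 1 average of at most 10 / 1.3 = 7.7. Subjects above that cannot meet it. At the entry floor of 3 it takes only 0.3 × 3 = 0.9 points.

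**The case against.** **The later paragraph is a study-specific carve-out.** It deals only with IBS, and a specific rule normally overrides a general one, including Section 8.6.4. This is a fair reading of intent. But it cancels a bullet that names IBS deterioration outright, in the same section, and nothing tells the reader to read it that way. The wording conflict stands.

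**Efficacy does capture worsening.** Section 4.2.1 first names pain intensity itself as the primary endpoint, and 8.6.1 says "worsening of IBS symptoms is captured as part of the efficacy parameter". A reader might infer from the responder definition that worsening is invisible in the plan. That goes too far. Section 9.4.3.1 models change from baseline in every 4-week period, and pain, stool, quality-of-life and work measures are summarized by arm (Sections 9.4.3.1 to 9.4.3.6), with minimum and maximum for continuous variables (Section 9.4.1). All data are listed. An average worsening could be seen; what is missing is a count of subjects who worsen.

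**Reports are handled centrally.** Section 8.6.5 sends them to one CRO team and refers to a Safety Monitoring Plan. This reduces inconsistency, but the team's stated task is severity and relatedness, and it still works from the conflicting definition.

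**A separate SAP is promised** (Section 9) and could contain such a table. The text available has none.

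**Two stronger inferences are not supported.** A reader might assume a baseline mean, a mean change and an SD and derive a number of AEs lost per arm. The documents give none of these, and the answer moves with the assumed response rate. AEs also arise from reports by subjects or investigators, not from diary averages, so a diary rise is not itself an AE. A reader might also infer that worsening IBS is the leading harm; Section 3.3.3 lists it among several unranked risks.

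**Conclusion.** The point holds. Section 8.6.1 contradicts itself on whether worsening IBS is an AE, and Section 8.6.4 adds a recording rule without an IBS exception. The stated justification does not hold for the binary responder. The mean-change analyses cover average shifts but not the number of subjects who worsen, so a named risk can be missing from the AE tables with no by-arm count elsewhere.

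No number of affected subjects can be derived from the documents. The step 4 illustration shows only that a worsened subgroup can be masked in a mean, and it depends on its assumed changes and variance. The primary test, sample size and power are unaffected. This should be corrected, but it does not threaten the primary efficacy conclusion.

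**What to change.** Reconcile the parts of Section 8.6.1 with each other and with Section 8.6.4 into one reporting rule, applied identically in both arms. Which rule to adopt is for the sponsor to decide.

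Whichever rule is chosen, add a by-arm summary from the existing diary data for weeks 1-4, 5-8, 9-12 and 13-16 and both long-term extension periods (weeks 35-38 and 61-64), giving:
- the distribution of change from Phase 1 in average worst pain;
- the number and percentage worsened by a pre-specified threshold that subjects with high baseline pain can also reach, for example an absolute rise alongside the 30% rise;
- the risk difference with 95% CI.

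Show beside each percentage how many subjects lack a derivable average under the 50% completeness rule of Section 9.4.1.

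The cost is a wording correction and one extra table. No new data are needed. The AE count may change, depending on the rule chosen.
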